| | 
 • High-risk person defined by: 
 • Age 18-44 with 2 or more comorbidities listed below • Age 45-79 with any comorbid condition listed below • Age 80 and above (regardless of comorbid conditions) • Co-morbid list 
 ○ Congestive Heart Failure (CHF) ○ Chronic lung disease[‡] ○ Solid organ transplant or immunosuppression* ○ Chronic Kidney Disease or End Stage Renal Disease ○ Diabetes mellitus ○ Cardiovascular disease/Hypertension ○ Smoking/Vaping (currently using or history of using in the past 1 year) ○ Obesity (calculated by height and weight per participant report) ○ Hyperlipidemia ‡Includes any of the following: asthma, chronic obstructive pulmonary disease, emphysema * Defined as an outpatient prescription of greater than 10 mg/day of prednisone or equivalent, use of chemotherapy, or use of immunosuppressive agents for solid organ transplant or for an autoimmune disease. • No current symptoms attributable to COVID-19 • No prior COVID-19 positive diagnosis (eligible if previous testing is negative and meets all other inclusion and exclusion) • Ability to provide informed consent • Confirmed review of concomitant medications (with emphasis on cardiac medications) |
| | 
Exclusion Criteria:
 
Exclusion Criteria Cohort A & B:
 
 • Known allergy to hydroxychloroquine or quinine • Known history of long QT syndrome • Known history of arrhythmia or dysrhythmia • Known current QTc >500 ms • Known G6PD deficiency • Known history of hypoglycemia • Pregnant or Nursing by patient history • Use of any of the following concomitant medications: See Appendix D for Exclusion medication list • Concurrent diagnosis of dermatitis, porphyria, or psoriasis • History of chronic liver disease, including cirrhosis and/or diagnosis of hepatitis (infectious, idiopathic, or immune) • History of chronic kidney disease • Pre-existing retinopathy • Already taking hydroxychloroquine • Any condition or medication in the opinion of the investigator that would prohibit the use of hydroxychloroquine • Enrollment in another clinical with investigational drug or device • Inability to swallow pills • Adults unable to provide informed consent |

| | |
|---------------------------|--|
| | |
| Sample Size | Cohort A n= 1356 Cohort B n= 383 |
| Study Intervention | Hydroxychloroquine vs. Placebo (Vitamin D with calcium) |

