6.3.10 Side Effects

1. Renal: Impairment of renal function with polyuria, nocturia, polydipsia, hypercalcemia, reversible azotemia, hypertension, nephrocalcinosis, generalized vascular calcification, or irreversible renal insufficiency which may result in death
2. Central Nervous System (CNS): Mental retardation, disorientation, confusion
3. Soft Tissues: widespread calcification of the soft tissues, including the heart, blood vessels, renal tubules, and lungs
4. Skeletal: Bone demineralization (osteoporosis) in adults. Decline in the average rate of linear growth and increased mineralization of bones in infants and children (dwarfism), vague aches, stiffness, and weakness
5. Gastrointestinal: Nausea, anorexia, and constipation
6. Metabolic: Mild acidosis, anemia, and weight loss
7. Teratogenic effects: supraaortic stenosis, elfin facies, and mental retardation recorded in pregnant women with hypervitaminosis D

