7.0 Participant Discontinuation/Withdrawal

Participants may withdraw consent at any time for any reason or be withdrawn from the trial at the discretion of the investigator should any untoward effect occur. In addition, a participant may be withdrawn by the investigator if enrollment into the trial is inappropriate, the trial plan is violated, or for administrative and/or other safety reasons.

7.1 Discontinuation of Study Intervention:

A participant must be discontinued from the trial for any of the following reasons:

- The participant withdraws consent.
- Intercurrent illness that prevents further administration of treatment
- The participant has a confirmed positive pregnancy test
- The participant is lost to follow-up

At the discretion of the investigator for safety, behavioral, compliance, or administrative reasons.

For those participants who discontinue study intervention early, each participant will be followed for 30 days for acute adverse event monitoring.

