8.2.2 Adverse Event (AE) Monitoring

The investigator or licensed designee (RN, CNP, pharmacist, or physician) on the study team will assess each participant to evaluate for potential new or worsening AEs as specified in the SoA and more frequently if clinically indicated. If participant reported symptoms are an AE, the event will be tracked as an AE.

Participants will be followed and accessed for acute AEs until day 35 (30 days after the last dose of study medication). AEs will be documented accordingly. Adverse events will also be assessed at the 12 month follow up visit.

8.3 Adverse events and Serious Adverse Events (SAE):

An AE is defined as any untoward or unfavorable medical occurrence in human participants, including any abnormal sign, symptom, or disease, temporally associated with the participant's participation in the research, whether considered related to the participant's participation in the research or not. AEs encompass both physical, psychological harms, and biochemical abnormalities. AEs may be reported by the participant, observed by the Investigator, or documented in medical records.

The site investigator and any licensed designees are responsible for detecting, documenting, and recording events that meet the definition of an AE or SAE and remain responsible for following up AEs that are serious, considered related to the study intervention or study procedures, or that caused the participant to discontinue the study treatment. The site investigator or licensed designee will evaluate all adverse events according to the National Cancer Institute (NCI) Common Terminology Criteria for Adverse Events (CTCAE) Version 5.0. Toxicities will be characterized in terms regarding grade (seriousness), causality/attribution (see section 8.3.2), and action taken with regard to trial intervention.

Any adverse event which changes CTCAE grade over the course of a given episode will have each change of grade recorded on the adverse event case report forms/worksheets.

If the adverse event meets any of the criteria below, it is regarded as a SAE:

- the event led to the death of the participant
- the event led to serious deterioration in the health of the participant, that either resulted in:
 - a life-threatening illness or injury
 - a permanent impairment of a body structure or a body function
 - in-patient or prolonged hospitalization

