The mutagenic potential of hydroxychloroquine was not evaluated. However, chloroquine has been shown to be a catalytic inhibitor of DNA repair enzymes (topoisomerase II) and to produce weak genotoxic effects through this mode of action.

Pregnancy - Teratogenic Effects: Human pregnancies resulting in live births have been reported in the literature and no increase in the rate of birth defects has been demonstrated. Embryonic deaths and malformations of anophthalmia and microphthalmia in the offspring have been reported when pregnant rats received large doses of chloroquine.

Nursing Mothers: Caution should be exercised when administering hydroxychloroquine sulfate tablets to nursing women. It has been demonstrated that hydroxychloroquine administered to nursing women is excreted in human milk and it is known that infants are extremely sensitive to the toxic effects of 4-aminoquinolines.

Pediatric Use: Safety and efficacy have not been established in the chronic use of hydroxychloroquine sulfate tablets for systemic lupus erythematosus and juvenile idiopathic arthritis in children. Children are especially sensitive to the 4-aminoquinoline compounds. Most reported fatalities followed the accidental ingestion of chloroquine, sometimes in small doses (0.75 g or 1 g in one 3-year-old child). Patients should be strongly warned to keep these drugs out of the reach of children (see OVERDOSAGE).

Geriatric Use: Clinical studies of hydroxychloroquine sulfate tablets did not include sufficient numbers of subjects aged 65 and over to determine whether they respond differently from younger subjects. However, this drug is known to be substantially excreted by the kidney, and the risk of toxic reactions to this drug may be greater in patients with impaired renal function. Because elderly patients are more likely to have decreased renal function, care should be taken in dose selection and it may be useful to monitor renal function.

ADVERSE REACTIONS: The following adverse reactions have been identified during post-approval use of hydroxychloroquine sulfate tablets or other 4-aminoquinoline compounds. Because these reactions are reported voluntarily from a population of uncertain size, it is not always possible to reliably estimate their frequency or establish a causal relationship to drug exposure.

Blood and Lymphatic System Disorders: Bone marrow failure, anemia, aplastic anemia, agranulocytosis, leukopenia, and

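### Harm confined to the fetus or child of an exposed participant has no defined capture and no route to the Safety Review Committee

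*Combined protocol and SAP*

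**What the plan says.** **Definitions (Section 8.3).** "An AE is defined as any untoward or unfavorable medical occurrence in human participants". An AE may be reported by the participant, observed, or found in medical records. The step to seriousness is: "If the adverse event meets any of the criteria below, it is regarded as a SAE". Three criteria follow. One is the participant's own death. Another is worded "the event led to serious deterioration in the health of the participant, that either resulted in"; its sub-items are illness or injury that threatens life, lasting impairment, and admission to hospital or a longer stay there. The last, an important medical event, is limited to intervention that prevents one of those outcomes.

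**Pregnancy.** The Synopsis excludes anyone "Pregnant or Nursing by patient history". Section 7.1 lists, among the reasons for discontinuation, "The participant has a confirmed positive pregnancy test". It then gives those who stop the intervention early 30 days of acute AE monitoring.

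**Contacts (Table 1; Sections 8.2.1, 8.2.2, 8.3.1).** After randomization there are calls at Days 3, 5, 14 and 35 and at 12 months. They cover COVID-19 symptoms (to Day 35), adverse events and COVID-19 outcome. Participants are also asked about any other symptoms. Acute AEs and SAEs are collected to Day 35. The 12-month assessment looks for events that could be attributed to hydroxychloroquine.

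**Reproductive text.** Appendix C states: "Embryonic deaths and malformations of anophthalmia and microphthalmia in the offspring have been reported", in rats given large doses of chloroquine. The sentence before it says that no rise in human birth defects has been demonstrated. For the vitamin D placebo, Section 6.3.10 lists teratogenic effects "recorded in pregnant women with hypervitaminosis D".

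**The concern.** The 24-hour report (8.3.2), the enrolment hold (8.3.1) and the SRC's receipt of SAEs (8.3.3) all start from an event that meets the AE or SAE definition. Harm that falls outside both definitions has no defined path to the people who decide whether the trial continues.

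A congenital anomaly is such a harm. The protocol raises the subject itself: it excludes pregnancy, makes a positive test a reason to discontinue, and prints reproductive findings for both products. It gives no means of learning that an exposed pregnancy occurred or how it ended. The safety report could then be silent on this outcome, and a reader could not tell whether nothing happened or nothing was asked.

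**Working it through.** No sample size, power or alpha figure bears on this point. The check is mainly a reading of the sections against one another, with one small calculation for context.

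**1. Can harm to the fetus or child be an AE?** The definition in 8.3 is confined to occurrences in participants. A fetus or infant is not a participant, so a malformation found only in the child is not an AE.

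**2. Can it be an SAE?** There are two obstacles. The list applies only to an event that is already an AE, and step 1 rules that out. The list also has no congenital-anomaly item: death and deterioration are each tied to the participant, and the important-medical-event item only reaches back to those outcomes.

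**3. Is there another route to the SRC?** The Study Chair's weekly review in 8.3.3 covers cumulative AEs and SAEs, so it inherits the same limit. The instruction in 8.3.2 to follow the most stringent rules concerns how SAEs are reported, not what counts as one.

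**4. Would the pregnancy be known?** Screening covers pregnancy by history only, so an unrecognised early pregnancy can pass. The eligibility criteria contain no contraception requirement. Table 1 has no pregnancy test and no pregnancy question at any of the five later contacts. Section 7.1 relies on a confirmed positive test that nothing in the schedule would prompt.

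**5. Would a known pregnancy be followed to its outcome?** The heading of 7.1 concerns the study intervention, but its text speaks of leaving the trial, and the only follow-up it states is 30 days. Table 1 and Section 4.2 take follow-up to 12 months. On the literal reading of 7.1, a participant with a positive test could be removed before the outcome is known. These sections do not agree.

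**6. Does exposure outlast acute AE collection?** Day 35 is 30 days after the last dose on Day 5. Under simple first-order decay, the fraction remaining is 0.5^(30/t), with t the half-life in days. Inputs are from Appendix C.

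| Half-life (days) | Source in Appendix C | Fraction at 30 days |
|---|---|---|
| 22.4 | single oral dose, blood | 0.5^(30/22.4) = 0.40 |
| 40 | lower terminal value, chronic dosing | 0.5^(30/40) = 0.59 |
| 50 | upper terminal value, chronic dosing | 0.5^(30/50) = 0.66 |
| 123.5 | same single-dose study, plasma | 0.5^(30/123.5) = 0.85 |

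The range is about 40% to 85%. It mixes single-dose with chronic values and blood with plasma, so it shows only that drug would still be present.

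**7. How many pregnancies?** The documents give no rate. As illustration only, 0.5%, 1% and 2% of 1356 + 383 = 1739 participants would be about 9, 17 and 35, roughly half of them on hydroxychloroquine under 1:1 randomization. These rates are assumptions. They are applied to everyone, including men and a Cohort B selected for comorbidity or age, so they may well be too high. The point does not depend on them.

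**The case against.** The strongest reply is that much pregnancy-related harm is already covered. A reader might infer that any harm to an exposed pregnancy escapes the AE and SAE definitions and never reaches the SRC. The documents do not support that. A miscarriage or obstetric complication is an untoward medical occurrence in the participant, hence an AE, and it is an SAE if it meets a listed criterion such as hospitalization. The SRC receives all SAEs, and the Study Chair's weekly review can bring other AEs to it. Only harm confined to the fetus or child is left without a path.

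Nor is it right that pregnancy is never asked about: screening covers it by history, and later calls invite any other symptoms. But an invitation to report symptoms is not a question about pregnancy or its outcome.

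A reader might also take the reproductive text as evidence that these products, as used here, are hazardous in pregnancy. The text does not go that far. The hydroxychloroquine passage stands under Precautions, concerns large chloroquine doses in rats, and follows a statement that no increase in human birth defects has been shown. The vitamin D text concerns hypervitaminosis D, and nothing in the protocol says that 12 tablets of 10 mcg would cause it. These qualifiers limit the weight of the point. They do not explain why the outcome should go uncollected.

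Finally, consent pages and case report forms are not available for this review, and the protocol refers to institutional policy and regulatory requirements. Pregnancy reporting may be handled there, which cannot be checked. The definitions in 8.3 would still need to agree with it.

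**Conclusion.** The point holds for harm confined to the fetus or child of an exposed participant. Under the protocol as written, such harm meets neither definition, no contact after enrolment is specified to find it, and it has no defined route to the SRC. Maternal events are already covered as AEs or SAEs.

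The number of pregnancies affected cannot be derived from the documents. The 40% to 85% of drug remaining 30 days after the last dose rests on first-order decay and on half-lives measured under differing conditions. It supports only the statement that exposure could extend past the close of acute AE collection. No conclusion about actual teratogenic risk follows.

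This is a gap in the safety definitions and follow-up. The primary endpoint, sample size, alpha and efficacy analysis are untouched. It merits correction because the rule as written would classify a birth defect as not reportable, and the correction is cheap.

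**What to change.** 1. **Section 8.3.** State that a congenital anomaly or birth defect in the fetus or child of a participant exposed to study drug is recorded as an AE and regarded as an SAE. An extra bullet in the SAE list would not be enough, because the list applies only to events that are already AEs.
2. **Table 1 and Section 8.3.1.** Add one question on pregnancy since first dose to the existing Day 35 and 12-month calls. Record the outcome in both arms, tabulate it by arm and send it to the SRC. State that this item is collected to the 12-month call, since acute collection ends at Day 35. With a window of 12 months ±30 days, that call falls after the due date of anyone already pregnant at dosing. A later conception may still be ongoing and should be recorded as such.
3. **Section 7.1.** Reconcile its heading, its text and its 30-day follow-up with the 12-month follow-up, so that a participant with a positive pregnancy test still receives the 12-month call unless consent is withdrawn. This concerns data collection only and leaves the rule on stopping study drug as it is.

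The cost is a sentence or two in 8.3 and 8.3.1, a clarification in 7.1, and slightly more data collection on two calls already scheduled. No test or visit is added.

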8.3.1 AE and SAE Collection and Reporting

All acute SAEs/AEs will be collected from the time the informed consent form (ICF) is signed until day 35. Follow-up of AEs will end either when the symptom or illness resolves completely, up to 30 days past the end of study participation (if ongoing at the time of study exit) or until the investigator determines that the event has stabilized and will not completely resolve. Participants will be assessed at the 12 month visit for any potential adverse events that could be attributable to hydroxychloroquine.

AEs to be reported include:

- All SAEs regardless of attribution
- All Cardiac AEs for Grade 2 and above that are attributed to intervention (possible, probable, and definite)
- All AEs grade 3 and above regardless of attribution

Enrollment will be held and the SRC committee will meet if the following occur:

- Any SAEs with an attribution of possible, probable, and definite
- Any Cardiac AEs for Grade 2 and above that are attributed to intervention (possible, probable, and definite)
- Any AEs grade 3 and above attributed to intervention (possible, probable, and definite)

The SRC will review safety data and determine if the study can continue.

8.3.2 AE/SAE Assessments

All AE and SAE reporting will be conducted in compliance Sanford Health Policy HRP 024 New Information.

AE assessments will be focused on body systems with potential known toxicities and well as other toxicities verbalized by the participant.

All AE and SAEs will be assigned causality by the Investigator in their relationship to the study medication based on the following categories:

- Definitely: clear evidence exists that the event was caused by the intervention
- Probably: reasonable probability exists that the event was caused by the intervention
- Possibly: reasonable possibility exists that the event may have been caused by the intervention
- Unlikely: evidence exists that the event was caused by other factors; although the relationship of the event to the intervention cannot be completely ruled out, is remote

- Unrelated: the cause of the event is known and the event is in no way related to any aspect of the intervention

SAEs must be reported to the lead site and study chair at [contact] as soon as possible, but no later than 24 hours from the day the study team became aware of the event. Follow-up reports may be required or requested by the lead site or regulatory agency and should be completed promptly.

IRB notification of SAEs is required per Sanford IRB reporting guidelines. Investigators and study personnel are responsible for knowing IRB reporting requirements. Reporting of SAEs, whether related or unrelated to the study participation, should follow the most stringent rules for reporting.

The date of onset of the event, the date the site staff became aware of the event and determined it met the criteria of an SAE, and the date the event resolved or no longer fit the criteria of SAE will be documented in the source document and in the EDC system.

8.3.3 Safety Review Committee (SRC)

An independent SRC will be established with experienced members, none of whom are participating as study investigators, to monitor and evaluate the safety of subjects, to maintain oversight of study data and to monitor progress of the study. The committee will initially meet monthly and more frequently if concerns of safety are noted. The findings of the SRC will be submitted to the IRB within 10 days after the meeting. All SAEs will be reported to the SRC as soon as possible after learning of the event.

The Study Chair will review cumulative AEs and SAEs weekly and will share concerns with the SRC. The SRC will make recommendations to the Study Chair regarding steps to ensure subject safety and the continued ethical integrity of the trial. The SRC will review interim study results and consider the overall risk and benefit to trial participants. The SRC will recommend to the Study Chair whether the trial should continue in accordance with the protocol.

9.0 Statistical Considerations

9.1 Statistical Hypothesis

There will be a 50% decrease (relative risk reduction) in the conversion to infected status within the treatment arm compared to the control arm.

9.2 Sample Size Determination

Cohort A:

It is expected that 10% of exposed healthcare workers will convert to infected status without intervention. The treatment arm will be assumed to have a conversion of 5% (50% relative reduction, 5% absolute risk reduction). Due to the uncertainty of this

trial, a conservative 10% drop out rate is included in the calculation. Under these assumptions (Treatment: 5% infected, Control: 10% infected, α : 0.0492, Power: 90%), the total sample size is 1356 patients (610 patients are needed in each arm + 10% dropout = 1356 total patients).

Cohort B:

It is expected that 30% of exposed high risk patients will convert to infected status without intervention. The treatment arm will be assumed to have a conversion of 15% (50% relative reduction, 15% absolute risk reduction). Due to the uncertainty of this trial, a conservative 10% drop out rate is included in the calculation. Under these assumptions (Treatment: 15% infected, Control: 30% infected, α : 0.0492, Power: 90%), the total sample size is 383 patients (172 patients are needed in each arm + 10% dropout = 383 total patients).

